SPC	Summary of Products Characteristics
SS	Safety Analysis Set
SUSAR	Suspected Unexpected Serious Adverse Reaction
Th	T helper cell
TNF- α	Tumor Necrosis Factor-Alpha
UV-A/B	Ultraviolet-A/B
VAS	Visual Analogue Scale

Table of Contents

1	PROTOCOL SUMMARY	6
2	STATISTICAL METHODOLOGY	11
2.1	GENERAL CONSIDERATIONS	11
2.2	SUBJECT POPULATION	12
2.2.1	Baseline Characteristics/Medical History	12
2.2.2	Case Disposition	12
2.2.3	Dose Regimen	13
2.2.4	Study Populations for Analysis	13
2.2.4.1	Full Analysis Set (FAS)	13
2.2.4.2	Safety Analysis Set (SAS)	13
2.2.4.3	Per-Protocol Set (PPS)	13
2.2.4.4	Subgroup Analyses	13
2.2.5	Study Assessment Time Points	13
2.2.6	Methods for Handling Missing Data	14
2.2.7	Safety Monitoring	15
2.2.8	Statistical Hypotheses	15
2.2.9	Sample Size Justification	15
2.2.10	Interim Analyses	15
2.2.11	Randomization/Unblinding	15
2.2.11.1	Randomization Methodology	15
2.2.11.2	Unblinding	16
2.2.12	Efficacy Analyses	16
2.2.12.1	Primary Endpoint	17
2.2.12.2	Secondary Endpoints	17
2.2.12.3	Exploratory Endpoints	19
2.2.13	Safety Analyses	22
2.2.13.1	Extent of Exposure	22
2.2.13.2	Safety Endpoint(s)	22
2.2.13.3	Adverse Events	22
2.2.13.3.1	Serious Adverse Events	23
2.2.13.3.2	Deaths	23
2.2.13.4.3	Interruptions or Discontinuations of Study Medication Due to an AE	23
2.2.13.4	Laboratory Data	24
2.2.13.5	Vital Signs, Physical Findings, and Other Observations Related to Safety	24
3	DOCUMENT VERSION CONTROL	25
	APPENDIX A - PROGRAMMING SPECIFICATIONS FOR TABLES AND LISTINGS	26

1 Protocol Summary

Title	A Randomised, Double-blind, Placebo-Controlled, Phase 2b Study to Assess the Efficacy and Safety of Orally Administrated DS107 in Patients with Moderate to Severe Atopic Dermatitis.
Study Objectives	
Efficacy Objective: To compare the efficacy of orally administrated DS107 versus placebo in the treatment of adult patients with moderate to severe Atopic Dermatitis (AD).
 
Safety Objective: To assess the safety of orally administrated DS107 versus placebo, in adult patients with moderate to severe AD.

Primary Endpoint	Proportion of patients achieving an Investigator’s Global Assessment (IGA) score of 0 (clear) or 1 (almost clear) and a decrease of at least 2 points in IGA in treated population compared to placebo population at Week 8.
Secondary Endpoint(s)	
 • Proportion of patients achieving an IGA score of 0 (clear) or 1 (almost clear) and a decrease of at least 2 points in IGA in treated population compared to placebo population from baseline to Week 2, 4, 6 and 10. • Proportion of patients achieving a decrease of at least 2 points in IGA in treated population compared to placebo population from baseline to Week 2, 4, 6, 8 and 10. • Change from baseline in Eczema Area and Severity Index (EASI) in treated population compared to placebo population at Weeks 2, 4, 6, 8 and 10. • Change from baseline in Numeric Rating Scale (NRS) for Pruritus in treated population compared to placebo population at Weeks 2, 4, 6, 8 and 10.
Exploratory Endpoints	
 • Time to response by Week 8. • Probability of being in response (PBIR) between Weeks 2 and 8. • Sustained efficacy between Weeks 8 and 10. • Change from baseline in the Dermatology Life Quality Index (DLQI) score in treated population compared to placebo population at Week 2, 4, 6, 8 and 10 and from Week 8 to Week 10.

	
 • Change from baseline in the Patient Orientated Eczema Measure (POEM) score in treated population compared to placebo population at Week 2, 4, 6, 8 and 10 and from Week 8 to Week 10. • Change from baseline in the Patient Global Impression of Severity (PGI-S) score in treated population compared to placebo population at Week 2, 4, 6, 8 and 10 and from Week 8 to Week 10. • Change from baseline in the Patient Global Impression of Change (PGI-C) score in treated population compared to placebo population at Week 2, 4, 6, 8 and 10 and from Week 8 to Week 10. • Plasma DGLA concentrations in treated population compared to placebo population at Baseline/Day 0, Week4, Week 8 and Week 10 (samples to be retained for the potential analysis at a later date). • Determination of AD biomarkers in treated population compared to placebo population at Baseline/Day 0 and Week 8/Early Termination (samples to be retained for the potential analysis at a later date).
Safety Endpoints	
 • Adverse event (AE) and serious adverse event (SAE) frequency and severity. • Safety laboratory parameters (haematology, clinical chemistry). • Clinical safety examinations (vital signs, physical examination).
Test Product, Dose and Mode of Administration	
All study medication will be blinded. DS107 capsules will be provided as a capsule containing 500 mg DGLA per unit dose. Placebo will be provided as a matching capsule. This study will involve two dose levels of DS107 for 8 weeks (1g DS107 OD or 2g DS107 OD) and a placebo control (OD)

Study Design:	
A minimum of 300 patients with moderate to severe AD will be included in this multicenter, double-blind, placebo controlled, 3arm, Phase IIb study. The sample size may be increased at an interim analysis (conducted after n=150 complete Week 8/Exit) to update primary efficacy endpoint assumptions and to achieve at least 80% power and two-sided 5% Type I error.
 
All patients will sign an informed consent and undergo screening for study eligibility. Patients will be randomized (1:1:1) at baseline visit to either receive 1g DS107 OD once daily or 2g DS107 OD

	
once daily or placebo once daily for 8 weeks.
 
Patients will come to the clinic on 7 separate visits: Screening, Baseline (Day0), Week 2, Week 4, Week 6, Week 8 (end of treatment) and Week 10 (follow-up). All patients will exit the study at the Week 10 visit.

Inclusion Criteria	
 1. Patients with a clinically confirmed diagnosis of active AD according to Hanifin and Rajka criteria. 2. Patients with moderate to severe AD at baseline as defined by an IGA score of minimum 3 at baseline visit. 3. Patients with an EASI score of ≥ 12 at screening and baseline. 4. Patients with AD covering a minimum 10% of the body surface area at baseline. 5. Patients whose pre-study clinical laboratory findings do not interfere with their participation in the study, in the opinion of the Investigator. 6. Patients who are able and willing to stop all current treatments for AD throughout the study (except for allowed emollients). 7. Patients who are on a stable dose of a bland emollient applied BD (twice daily) for at least 7 days prior to baseline. 8. Male or female patients aged 18 years and older on the day of signing the informed consent form (ICF). 9. Female patients and male patients with female partners of child bearing potential must use adequate contraception or have a sterilized partner for the duration of the study. Adequate contraception is defined as: systemic hormonal contraceptives, intrauterine device or barrier method of contraception in conjunction with spermicide, or agree to sexual abstinence. Hormonal contraceptives must be on a stable dose for at least one month before baseline. 10. Patients who are able to communicate well with the Investigator, to understand and comply with the requirements of the study, and understand and sign the written informed consent.
Exclusion Criteria	
 1. Patients with other skin conditions that might interfere with AD diagnosis and/or evaluation (such as psoriasis or current active viral, bacterial and fungal topical skin infections) as assessed by the Investigator. 2. Patients who have used systemic treatments (other than biologics) that could affect AD less than 4 weeks prior to baseline visit (Day 0), e.g. retinoids, methotrexate, cyclosporine, hydroxycarbamide (hydroxyurea), azathioprine and oral/injectable corticosteroids. Intranasal corticosteroids and inhaled corticosteroids for stable medical conditions are allowed.

	
3. Patients who have used any topical medicated treatment for AD two weeks prior to start of treatment/baseline (Day 0) including but not limited to, topical corticosteroids, calcineurin inhibitors, tars, bleach, antimicrobials and bleach baths.4. Patients who use topical products containing urea, ceramides or hyaluronic acid two weeks prior to Day 0.5. Patients who use anti-histamines for AD within 3 days of baseline. Non-sedative anti-histamines for other indications may be used throughout the study provided the patient is on a stable dose for 4 weeks prior to Baseline.6. Patients with the presence of an irregular white cell count as evidenced by eosinophils $> 0.3 \times 10^9 /L$ at the screening visit.7. Patients who have had excessive sun exposure, have used tanning booths or other ultraviolet (UV) light sources four weeks prior to baseline (Day 0) and/or are planning a trip to a sunny climate or to use tanning booths or other UV sources between screening and follow-up visits.8. Patients who have a history of hypersensitivity to any substance in DS107 or placebo capsules.9. Patients who have any clinically significant controlled or uncontrolled medical condition or laboratory abnormality that would, in the opinion of the Investigator, put the patient at undue risk or interfere with interpretation of study results.10. Patients who have a clinically significant impairment of renal or hepatic function.11. Patients with significant uncontrolled cardiovascular, neurologic, malignant, psychiatric, respiratory or hypertensive disease, as well as uncontrolled diabetes and floride arthritis or any other illness that, in the opinion of the Investigator, is likely to interfere with completion of the study.12. Patients with chronic infectious diseases (e.g., hepatitis B, hepatitis C or infection with human immunodeficiency virus).13. Patients with a history of clinically significant drug or alcohol abuse in the opinion of the Investigator in the last year prior to baseline (Day 0).14. Patients who have participated in any other clinical study with an investigational drug within 3 months before the first day of administration of study treatment.15. Patients who have had treatment with biologics as follows: a. Any cell-depleting agents including but not limited to rituximab: within 6 months before the screening visit, or until lymphocyte count returns to normal, whichever is longer, b. Other biologics influencing cell proliferation: within 6 months before the screening
--	--

	
visit.
 
16. Patients who are pregnant, planning pregnancy, breastfeeding and/or are unwilling to use adequate contraception (as specified in inclusion criterion 7) during the trial.
 
17. Patients, in the opinion of the Investigator, not suitable to participate in the study.

--	---

2 Statistical Methodology

2.1 General Considerations

The objective of this double-blinded Phase 2b study is to assess the efficacy and safety of orally applied DS107 to adults with moderate to severe Atopic Dermatitis. This study uses a randomized (1:1:1, Treatment group A: 1g DS107, Treatment group B: 2g DS107 and Treatment group C: Placebo), double-blind, placebo-controlled parallel group design. Disposition, compliance, demographics, and primary and secondary efficacy results will be presented by treatment group separately for moderate and severe AD as well as for combined groups.

Study medication will be orally applied once daily for 8 weeks. An End of Therapy (EOT) visit will occur at Week 8 for subjects who complete 8 weeks of treatment or earlier if the subject discontinues from the study prematurely. An End of Study (EOS) visit will be conducted at 10 weeks post-treatment for all subjects, even if they withdrew early. For subjects who discontinue early, they will also be asked to return two weeks later for the safety assessments listed at Week 10/Visit 7.

All subjects screened into the study will be assigned a patient identifier number during screening that will be used on all patient documentation. The patient identifier number will contain the site number and the patient number assigned in numerical order at the screening visit (e.g.: 102-10 for the tenth patient screened at the site number 102). Patient numbers will be assigned in ascending order starting with 01. All data will be listed in subject data listings sorted by site and subject number unless otherwise noted. Data tabulations will be prepared as described in the sections below.

All statistical processing will be performed using Statistical Analysis System (SAS®) Version 9.3 or higher, unless otherwise noted. All analyses will be conducted in accordance with ICH E6 and E9 standards and applicable Contract Research Organisation (CRO) Standard Operating Procedures (SOPs). CDISC and SDTM data conventions will be followed; these data sets will include DLQI scoring performed by the data management group and provided to CTDS in the SDTM datasets.

The 2g DS107 treatment group will be tested against the placebo group using a hierarchical approach and if significant at the 0.05 level, then the 1g DS107 treatment group will be tested against the placebo at the 0.05 level, otherwise these will be presented as descriptive statistics.

Baseline values will be defined as the last non-missing measurement prior to dosing with study drug (where baseline record flag='Y' in datasets), unless otherwise specified. Change from baseline will be defined as the post-baseline visit value minus the baseline or previous value unless otherwise specified.

2.2 Subject Population

2.2.1 Baseline Characteristics/Medical History

Demographics - gender, age, race (years), ethnicity, country, weight, height, BMI and baseline BSA will be summarized by treatment group for the Full analysis set (FAS) population. Demographics will be displayed separately for the moderate and severe AD as well as overall.

P-values will be provided for the overall global test and each placebo pair (1g DS107 compared to placebo and 2g DS107 compared to placebo) and for comparison of 2g DS107 to 1g DS107. Binary measures (Gender, ethnicity, country and Race—white vs non-white) will be compared using a two-sided Fisher Exact test, while continuous measures (age, weight, height, BMI and baseline BSA) will be compared using ANOVA with Tukey option for the comparison of differences in means between the groups.

Medical History will be tabulated descriptively, including severity of AD, duration of AD (acute, intermediate or chronic) and other relevant medical history. The specific AD medical history reported terms and areas affected will be provided in the listings as text fields.

2.2.2 Case Disposition

All subjects enrolled into the study that are issued a subject number will be accounted for in Subject Disposition. Data will be tabulated by treatment group and the numbers and percentages of subjects in each treatment group who are enrolled, randomized and treated, who comprise the Full Analysis Set (FAS), Safety Analysis Set (SS), and the Per-Protocol Analysis Set (PPS) if there is a >10% loss relative to the FAS analysis populations, and who complete the study or withdraw prematurely along with the reason for discontinuation will be presented. The number of subjects who were seen at each specified study visit will also be tabulated by treatment group and by site. Results will be displayed separately by moderate and severe AD as well as overall.

Protocol deviations (major and minor) will be defined prospectively and will be presented as a listing by treatment group. Major protocol deviations will be tabulated by treatment group.

Reasons for any early withdrawals and the last treatment visit completed prior to discontinuation will be provided in a listing.

2.2.3 Dose Regimen

The following three formulations have identical appearance: 1g DS107, 2g DS107 and Placebo in a 1:1:1 ratio, respectively. The medication assigned by randomization will be orally applied by the patients once daily for 8 weeks. Tabulations of exposure to study medication are described in Section 2.2.13.1, Extent of Exposure. Details of study medication use will be provided in a subject data listing.

2.2.4 Study Populations for Analysis

2.2.4.1 Full Analysis Set (FAS)

The FAS consists of all patients who are randomized to the study and received at least one dose of study medication. FAS is the primary analysis population for efficacy endpoints. Analysis will be done according to the treatment patients were randomized to.

2.2.4.2 Safety Analysis Set (SS)

The SS consists of all patients who received at least one dose of the medication. SS is the analysis population for all safety endpoints. Analysis will be done according to the actual treatment patients received.

2.2.4.3 Per-Protocol Analysis Set (PPS)

The PPS is the subset of FAS who completed the study without any major violations. Protocol violations will be assessed for each patient in a blinded fashion prior to database lock at a Blind Data Review Meeting (BDRM), and the PPS will also be finalized during this meeting. PPS is a supportive analysis population for the primary efficacy endpoint. Analysis will be done according to the treatment that patients were randomized to.

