STUDY DURATION:	10 weeks (Treatment Duration: 8 weeks)
INVESTIGATIONAL PRODUCT:	DS107 capsules Placebo
OBJECTIVE:	
Efficacy objective:
 
To compare the efficacy of orally administered DS107 versus placebo, in the treatment of adult patients with moderate to severe Atopic Dermatitis (AD).
 
Safety objective:
 
To assess the safety of orally administered DS107 versus placebo, in adult patients with moderate to severe AD.

PRIMARY ENDPOINT:	Proportion of patients achieving an Investigator's Global Assessment (IGA) of 0 (clear) or 1 (almost clear) and a decrease of at least 2 points in IGA in treated population compared to placebo population at Week 8.
SECONDARY ENDPOINTS:	
 • Proportion of patients achieving an IGA score of 0 (clear) or 1 (almost clear) and a decrease of at least 2 points in IGA in treated population compared to placebo population from baseline to Week 2, 4, 6 and 10. • Proportion of patients achieving a decrease of at least 2 points in IGA in treated population compared to placebo population from baseline to Week 2, 4, 6, 8 and 10. • Change from baseline in Eczema Area and Severity Index (EASI) in treated population compared to placebo population at Week 2, 4, 6, 8 and 10. • Change from baseline in Numeric Rating Scale (NRS) for Pruritus in treated population compared to placebo population at Week 2, 4, 6, 8 and 10.
EXPLORATORY ENDPOINTS:	
 • Change from baseline in the Dermatology Life Quality Index (DLQI) score in treated population compared to placebo population at Week 2, 4, 6, 8 and 10. • Change from baseline in the Patient Orientated Eczema Measure (POEM) score in treated population compared to

	
placebo population at Week 2, 4, 6, 8 and 10.
 
 • Change from baseline in the Patient Global Impression of Severity (PGI-S) score in treated population compared to placebo population at Week 2, 4, 6, 8 and 10. • Change from baseline in the Patient Global Impression of Change (PGI-C) score in treated population compared to placebo population at Week 2, 4, 6, 8 and 10. • Plasma DGLA concentrations in treated population compared to placebo population at Baseline/Day 0, Week 4, Week 8 and Week 10 (samples to be retained and analysed for the potential analysis at a later date). • Determination of AD biomarkers at Baseline/Day 0, and Week 8 (samples to be retained for the potential analysis at a later date).

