7.5.2 Withdrawals from Investigational Product

Discontinuation of investigational product, but continued follow-up visits, including efficacy and safety evaluations. Standard reasons for withdrawing from taking further investigational product, but continuing follow-up visits and safety evaluations may be:

- Unacceptable adverse events
- Patient request
- Investigator’s discretion
- Intercurrent illness
- Lack of efficacy
- Pregnancy

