12.7 Analysis Populations

Enrolled Population

The Enrolled Population consists of all patients who sign informed consent.

Screen Failures

Screen Failures are patients from the Enrolled Population who do not meet the eligibility requirements and are withdrawn from the study prior to Randomisation.

Randomised Population

The Randomised Population consists of all patients who are randomised to the study.

Safety Analysis Set (SAS)

The Safety Analysis Set (SAS) consists of all patients who received at least one dose of the medication. SAF is the analysis population for all safety endpoints. Analysis will be done according to the actual treatment patients received.

Full Analysis Set (FAS)

The Full Analysis Set (FAS) consists of all patients who are randomised to the study and received at least one dose of study medication. FAS is the primary analysis population for efficacy endpoints. Analysis will be done according to the treatment patients were randomised to.

Per Protocol Set (PPS)

The Per Protocol Set (PPS) is the subset of FAS who completed the study without any major violations. Protocol violations will be assessed for each patient in a blinded fashion prior to database lock at a Blind Data Review Meeting (BDRM), and the PPS will also be finalised

during this meeting. PPS is a supportive analysis population for efficacy endpoints. Analysis will be done according to the treatment patients were randomised to.

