2.2.5 Study Assessment Time Points

The study consists of seven protocol-specified visits which will be assessed as nominal visits from an analysis perspective:

- Visit 1/Screening visit (Day -30 to -1): Once informed consent has been obtained, the Investigator will assign a Patient Number and the subject will undergo the screening procedures. Following completion of a successful screening visit, patients will begin the comparative treatment period (8 weeks).
- Visit 2/Baseline (Day 0): At the start of the comparative treatment period, after confirmation of continued eligibility, patients will be randomly assigned to one of the three treatment regimens. Study medication is dispensed at Visit 2. The first dose of study medication will be carried out at the site once all baseline assessments have been completed. The patient will carry out their second dose of study medication in the evening of Day 0.
- Visits 3, 4 and 5: Follow-up visits at Week 2 (Day 14 ± 2 days), Week 4 (Day 28 ± 2 days) and Week 6 (Day 42 ± 2 days) respectively.
- Visit 6 – End of Treatment (EOT): Week 8 (Day 56 ± 2 days) for subjects who complete 8 weeks of treatment; earlier for subjects who discontinue treatment prematurely.
- Visit 7/Week 10: End of Study visit (Day 70 ± 3 days) for all subjects.
- Unscheduled Visits: Unscheduled visits may occur when a patient needs to make a visit in between the scheduled visit dates due to an AE, difficulty complying with the study protocol requirements, or a significant change in their disease state. All procedures that are medically necessary should be followed.

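### Per-protocol set for a Week 8 endpoint is tied to completing a study that ends at Week 10, and states no exposure or compliance criterion

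*SAP*

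**What the plan says.** SAP 2.2.4.3 defines the per-protocol set (PPS) in one sentence: "The PPS is the subset of FAS who completed the study without any major violations". Protocol 12.7 has the same definition: "The Per Protocol Set (PPS) is the subset of FAS who completed the study without any major violations". Both add that violations are assessed at a blinded data review meeting before database lock, where membership is finalised.

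Neither document defines study completion. The Protocol synopsis gives a study duration of 10 weeks and a treatment duration of 8. The SAP protocol summary states "All patients will exit the study at the Week 10 visit", and SAP 2.2.5 lists "Visit 7/Week 10: End of Study visit (Day 70 ± 3 days) for all subjects".

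The primary endpoint is IGA response at Week 8. SAP 2.2.12.1 analyses it on the full analysis set (FAS) and repeats it on the PPS as support, with no condition attached. SAP 2.2.2, on disposition, refers to "the Per-Protocol Analysis Set (PPS) if there is a >10% loss relative to the FAS analysis populations".

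Protocol 7.5.2 describes a withdrawal category in which drug stops and visits do not: "Discontinuation of investigational product, but continued follow-up visits, including efficacy and safety evaluations".

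SAP 2.2.2 promises a prospective definition of major and minor deviations, but neither document lists them. SAP 2.2.13.1 calculates percentage compliance without setting a threshold or linking it to the PPS.

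**The concern.** A per-protocol analysis is meant to show the effect in patients treated and assessed as planned, up to the time the endpoint is measured. This definition falls short in two ways.

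First, membership can depend on something that happens after the endpoint. A missed Week 10 visit says nothing about how well Weeks 0 to 8 followed the plan. If attendance at Week 10 is related to Week 8 response, and differently by arm, conditioning on it can also bias the comparison.

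Second, the one feature that should separate the PPS from the FAS, adherence to treatment, does not appear in the definition. It is left to a list of major deviations that is not in the documents.

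Protocol 12.9.2 interprets the primary effect as the one to expect when the medication is taken as directed, and repeats that analysis on the PPS. A PPS that may contain patients off drug is weak support for that interpretation. The other check on the primary result in the SAP, the extreme-case analysis in 2.2.6, deals with missing outcomes and not with adherence.

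**Working it through.** **1. Which visit completes the study?**

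| Source | Points to |
|---|---|
| Protocol synopsis: study 10 weeks, treatment 8 | Week 10 |
| SAP protocol summary: all patients exit at Week 10 | Week 10 |
| SAP 2.2.5: Visit 7 is the End of Study visit | Week 10 |
| Protocol 8.1: Visit 7 is also scheduled for patients who do not complete the study | Completion settled before Visit 7 |
| SAP 2.1: End of Study visit also held for early withdrawals | Attending it does not by itself mark completion |
| SAP 2.2.6 and 2.2.10: Week 8 is labelled as exit | Week 8 |

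The statements about duration and exit favour Week 10. The others make the term ambiguous, so two programmers could build different sets.

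**2. Is adherence covered?** The definition names no minimum exposure, compliance level or valid Week 8 IGA. Protocol 7.5.2 allows a patient to stop drug and keep attending, and Protocol 11.4 gives one situation in which that is foreseen. Whether such a patient is in the PPS depends on the unlisted major-deviation criteria, and on whether an early End of Treatment visit (SAP 2.2.5) counts as completing.

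**3. The plan's own power figure.** Protocol 12.3 gives 21.6% versus 11.8%, 100 per arm, 5% significance and 45% power. The Protocol synopsis makes tests two-sided. For a two-proportion test with difference d, power = Φ[(d − 1.96·SE0)/SE1].
- Mean rate = (0.216 + 0.118)/2 = 0.167
- SE0 = √(2 × 0.167 × 0.833/100) = 0.0527
- SE1 = √((0.216 × 0.784 + 0.118 × 0.882)/100) = 0.0523
- (0.098 − 0.1034)/0.0523 = −0.103, so power = 45.9%, which agrees with the stated 45%

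With the SAP 2.2.9 inputs (10% placebo, 15-point difference, 100 per arm) the same formula gives 80.2%. This simple test stands in for the planned repeated-measures model, so the figures below measure lost information and do not predict the actual analysis.

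**4. Patients lost only for a missed Week 10 visit** (assumed loss, response rates unchanged):

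| Loss | Of 300 | n per arm | Power, Protocol rates | Power, SAP rates |
|---|---|---|---|---|
| 0% | 0 | 100 | 45.9% | 80.2% |
| 5% | 15 | 95 | 44.0% | 78.1% |
| 10% | 30 | 90 | 42.1% | 75.9% |
| 15% | 45 | 85 | 40.2% | 73.4% |

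**5. Drug-stoppers included in the PPS.** Assume a fraction s of each active arm's PPS stopped drug and responds at the placebo rate. The difference becomes (1 − s) × d.

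| s | Protocol rates, d = 9.8 points | SAP rates, d = 15 points |
|---|---|---|
| 5% | 9.3 | 14.25 |
| 10% | 8.8 | 13.5 |
| 20% | 7.8 | 12.0 |

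**6. The >10% clause.** With an FAS of 300, 10% is 30 patients. If 15 were lost (5%), the SAP 2.2.2 condition would not be met, yet SAP 2.2.12.1 would still run the PPS analysis. It could then be reported with no PPS count in the disposition table.

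**The case against.** The strongest reply is that the definition works once the blinded meeting has done its job. Major deviations are to be set prospectively, the meeting can class early discontinuation as one, and membership is fixed before unblinding. The SAP also sometimes treats stopping drug as leaving the study: 2.1 moves the end-of-therapy visit forward for early discontinuation from the study, 2.2.5 does so for early discontinuation of treatment, and 2.2.13.3 pairs drug withdrawn with stopping participation. On that usage a drug-stopper is not a completer and is out. The wording in Protocol 8.1 and SAP 2.1, 2.2.6 and 2.2.10 also leaves room for completion to mean Week 8.

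Much of this stands. A reader might infer that patients who stop drug but attend every visit are kept, because Protocol 7.5.2 allows it and it is therefore no violation, and so that the rule is backwards. The documents do not support that. Permission to keep attending does not settle how a deviation is graded, and the criteria are not given. Inclusion is possible but not established.

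The reply does not remove the problem. The Week 10 reading remains the natural one, and a blinded review applying the written definition would have to exclude a fully treated patient who missed Visit 7. Nothing written tells the meeting how to class drug discontinuation or what compliance to require.

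A further fair point is that one PPS output does need Week 10: the Week 8 to Week 10 shift table in SAP 2.2.12.3. That justifies a data requirement for that table, not for membership of the set.

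**Conclusion.** The point holds in a limited form. Study completion is the wrong anchor for a set that supports a Week 8 endpoint, and the adherence criterion is unspecified. The conflict between SAP 2.2.2 and SAP 2.2.4.3 and 2.2.12.1 over the >10% condition is a smaller, separate inconsistency that should be settled in the same edit.

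The consequence is confined to a supportive analysis. The FAS is primary, PPS membership is decided blind, and no decision rule uses the PPS. The sizes in the working are illustrative, because the documents give no rate for missed Week 10 visits or for stopping drug while attending. The power loss assumes that response rates are the same in those lost and those retained. The diluted difference assumes that drug-stoppers respond at the placebo rate and that the blinded review removes none of them. The change is worth making before database lock because it costs almost nothing.

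**What to change.** Redefine the PPS in SAP 2.2.4.3, with a matching sentence in Protocol 12.7, as FAS patients who have:
- an IGA within the Week 8 visit window;
- compliance through Week 8 at or above a level fixed blind before database lock;
- no major deviation up to Week 8.

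State that premature discontinuation of study drug excludes a patient from the PPS, and remove the requirement to complete Week 10. Run the Week 8 to Week 10 PPS shift table on PPS patients who have Week 10 data. Delete the >10% clause in SAP 2.2.2, or reconcile it with SAP 2.2.4.3 and 2.2.12.1.

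Before a compliance level is set, the denominator in SAP 2.2.13.1 needs reconciling. It expects 14 doses per two weeks and attributes this to twice-daily dosing, while the same section describes once-daily dosing.

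The cost is a few sentences in the SAP and one in the Protocol, with no new data collection. The PPS may be slightly smaller if many patients stop drug.
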